6.2.1 Specimen Submission Using the Alliance Biospecimen Management System

USE OF THE ALLIANCE BIOSPECIMEN MANAGEMENT SYSTEM (BioMS) IS MANDATORY AND ALL SPECIMENS MUST BE LOGGED AND SHIPPED VIA THIS SYSTEM.

BioMS is a web-based system for logging and tracking all biospecimens collected on Alliance trials. Authorized individuals may access BioMS at the following URL: <http://bioms.allianceforclinicaltrialsinoncology.org> using most standard web browsers (Safari, Firefox, and Internet Explorer). For information on using the BioMS system, please refer to the 'Help' links on the BioMS webpage to access the on-line user manual, FAQs, and training videos. To report technical problems, such as login issues or application errors, please contact: [REDACTED]. For assistance in using the application or questions or problems related to specific specimen logging, please contact: [REDACTED].

After logging collected specimens in BioMS, the system will create a shipping manifest. This shipping manifest must be printed and placed in the shipment container with the specimens.

All submitted specimens must be labeled with the protocol number (A021501), Alliance patient ID number, patient's initials, date and type of specimen collected (e.g. serum, whole blood).

A copy of the Shipment Packing Slip produced by BioMS must be printed and placed in the shipment with the specimens.

Instructions for the collection of specimens are included below. Please be sure to use a method of shipping that is secure and traceable. Extreme heat precautions should be taken when necessary.

Ship specimens on Monday through Thursday only. Shipping by overnight service to assure receipt is encouraged. Do not ship specimens on Fridays or Saturdays.

All specimens should be sent to the following address:

Alliance Biorepository at Washington University (WUSTL)
BJC Institute of Health

6.2.2 Tissue Collection and Processing for Histopathology Review

Consistent and accurate histologic grading is important for this study. Submission of tumor paraffin blocks, cores, or slides (see below) from the patient's surgical resection is required for all patients enrolled to this study. If the resection specimen shows pCR, then submission of the pretreatment/diagnostic fine needle aspiration (FNA) or core biopsy is also required (if possible).

The pretreatment diagnosis of pancreatic adenocarcinoma will be established by either fine needle aspiration (FNA) cytology or core needle biopsy. All patients must undergo local pathology review of the FNA/core biopsy for confirmation of diagnosis prior to registration. Central pathology review of the pretreatment specimen is not required prior to registration. It is anticipated that the pretreatment diagnosis of pancreatic adenocarcinoma will be established by fine needle aspiration (FNA) cytology in most cases. Less commonly, core needle biopsy may have been performed for initial diagnosis.

Following protocol surgery, in the event that the surgical pathology report of the resected tumor demonstrates no pathologic evidence of malignancy (i.e. pathologic complete response; pCR) or an unexpected histology other than adenocarcinoma, the pretreatment diagnostic cytology/pathology specimens and representative slides of the resected post-treatment specimen will be requested and reviewed at The Ohio State University by the Pathology Co-Chair.

For all patients who undergo surgery, the following specimens are required to be submitted within 60 days of surgical resection:

- One stained H&E slide from the surgical resection specimen
- A paraffin-embedded block or block-alternative (as many unstained slides as possible, up to 10) from the surgical resection specimen

For patients whose resection specimen shows pCR or an unexpected histology other than adenocarcinoma, the following specimens are required (if possible) to be submitted within 60 days (in addition to the surgical resection specimen):

- One stained H&E slide from the pretreatment FNA/core biopsy tissue
- A paraffin-embedded block or block alternative (as many unstained slides as possible, up to 10) from the pretreatment FNA/core biopsy tissue

For patients who consent to biobanking for future research and whose resection specimen does not show pCR or an unexpected histology other than adenocarcinoma, if possible, please submit the following within 60 days of surgical resection:

- A paraffin-embedded block or block alternative (as many unstained slides as possible, up to 10) from the pretreatment FNA/core biopsy tissue

The de-identified surgical pathology report, coded with the Alliance patient ID number, must accompany all tissue specimen submissions. Usually, this is generated by obscuring all PHI (names and dates) with white-out or a black magic marker, labeling each page of the report with the Alliance patient ID, and photocopying the report.

For patients who consent to future unspecified research (model consent question, “My samples and related information may be kept in a Biobank for use in future health research”) any unused tumor tissues from histology review will be stored at the Alliance Biorepository for later use.

Block Alternatives: The Alliance has instituted special considerations for the small percentage of hospitals whose policy prohibits long-term storage of blocks, and the smaller percentage of hospitals whose policies prohibit release of any block. If, due to institutional policy, a block cannot be sent, one stained and 10 unstained slides (or as many as possible) (thickness of 4-5 micron) will be sent to the Alliance Biorepository (WUSTL). **However, blocks are strongly preferred over slides.**

All unstained slides should be labeled with **thickness** (e.g. 5 micron), the specimen surgical pathology number, and block number either via your institution’s standard method for labeling clinical slides or using a permanent marker. **Labeling with sticky labels is not acceptable.**

The goal of the Alliance Biorepository is to provide investigators with quality histology sections for their research while maintaining the integrity of the tissue. For these reasons it is preferred that the Alliance Biorepository bank the block until

the study investigator requests thin sections. Please contact the Alliance Biorepository if additional assurances with your hospital pathology department are required.

6.2.3 Blood Specimen Submission for A021501-PP1

For patients who consent to participate, whole blood specimen will be used for the pharmacogenomic studies described in [Section 14.1](#). This specimen should be collected prior to the initiation of protocol treatment.

Collect 10 mL of peripheral venous blood in an EDTA (lavender) tube. The tubes should be inverted several times to mix the EDTA and refrigerated until shipped on cool pack by overnight mail to the Alliance Biorepository at Washington University (WUSTL). The specimens should be shipped the same day that the blood is drawn in ambient temperature per [Section 6.2.1](#).

Label specimens with the following identification information:

1. Procurement Date and Time
2. Patient Initials
3. Alliance Patient ID Number
4. Alliance Study Number (i.e. A021501-PP1)
5. Sample Type (i.e. Whole Blood)

Ship blood per instructions in [Section 6.2.1](#).

6.3 Submission of Digital Radiation Therapy Data

Note: Arm 2 closed to new patient enrollment on 08/13/2018.

6.3.1 Digital RT Data Submission Requirements

Submission of treatment plans in digital format as DICOM RT is required. Digital data must include CT scans, structures, plan, and dose files. This study uses TRIAD for RT data submission. Use of TRIAD requires several preliminary steps. See [Section 4.1.1](#) for details. Additional information is available at: <http://triadhelp.acr.org/ClinicalTrials/NCISponsoredTrials.aspx>

In the event that a site has not completed all steps required for TRIAD data submission in time to meet the timeline for pre-treatment review, data submitted via SFTP will also be accepted. See the instructions for submission of data via SFTP on the IROC Rhode Island website under Digital Data.

Any items on the list below that are not part of the digital submission may be included with the transmission of the digital RT data.

One week prior to the start of radiotherapy, the following data shall be submitted for pre-treatment review:

6.3.1.1 Treatment Planning System Output

RT treatment plans including CT, structures, dose and plan files. These items are included in the digital plan.

Dose volume histograms (DVH) for the composite treatment plan for all target volumes and required organs at risk. For all RT plans, a DVH shall be submitted for a category of tissue called “unspecified tissue.” This is defined as tissue contained within the skin, but which is not otherwise

identified by containment within any other structure. DVHs are included in the digital plan.

Digitally reconstructed radiographs (DRR) for each treatment field, showing the collimator and beam aperture. Please include two sets, one with and one without overlays of the target volumes and organs at risk. Please have the fiducial markers included in the DRRs that are used for set-up.

Treatment planning system summary report that includes the monitor unit calculations, beam parameters, calculation algorithm, and volume of interest dose statistics.

6.3.1.2 Supportive Data

The following data is to be submitted to IROC Rhode Island:

- Prescription sheet for entire treatment.
- If the recommended doses to the organs at risk are exceeded, an explanation should be included for review by IROC Rhode Island and the radiation oncology reviewers.

6.3.1.3 Forms

The following forms are to be submitted to IROC Rhode Island:

- RT-1 Dosimetry Summary Form
- Motion Management Reporting Form
- Within 21 days of the completion of radiotherapy, the following data shall be submitted for all patients:
 - The RT-2 Radiotherapy Total Dose Record Form
 - A copy of the patient's radiotherapy record including the prescription, and the daily and cumulative doses to all required areas.
 - Documentation listed above showing any modifications from the original submission.

Supportive data and forms may be included with the transmission of the digital RT data or submitted separately via e-mail or mailed to:

IROC Rhode Island QA Center

[Redacted]

Questions regarding the dose calculations or documentation should be directed to:

Protocol Dosimetrist
IROC Rhode Island QA Center

[Redacted]

6.4 Imaging Requirements, Credentialing, and Submission Instructions

6.4.1 Institutional Imaging Credentialing Procedures

Prior to the enrollment of patients on A021501, institutions must be credentialed by the Alliance Imaging Core Laboratory (ICL) at The Ohio State University Medical Center (also known as IROC Ohio). If the site is already credentialed by the ICL to participate in imaging studies, the ICL will provide a brief A021501 protocol refresher prior to the site enrolling patients on this trial.

See [Section 15.1.1](#) for further details

6.4.2 CT Submission Instructions

The following images and local interpretation reports will be collected digitally and submitted for centralized, **real-time re-review** (in addition for the A021501-IM1 correlative study and for banking purposes):

- Baseline (within 28 days prior to patient registration): This scan will be reviewed centrally to ensure that patient meets the criteria for borderline resectable disease, as detailed in [Section 3.2.1](#) and [Appendix II](#).
- Pre-Surgery Restaging:
 - i) Arm 1 (after 8 cycles of mFOLFIRINOX and prior to surgery).
 - ii) Arm 2 (after 7 Cycles of mFOLFIRINOX + Radiotherapy and prior to surgery)

This scan will be reviewed centrally to determine if the patient has potentially resectable disease and is appropriate for surgical intervention, at completion of preoperative therapy.

For patients who consent to the imaging study A021501-IM1 (model consent question, “I agree to have my scan images be collected and submitted for the research stated above”), the following scans and local interpretation reports should also be submitted to the IROC Ohio Imaging Core Lab (ICL) for the A021501-IM1 correlative study and banking purposes. These scans may be batched shipped every 6 months:

- Post 4 cycles of mFOLFIRINOX (See [Section 5.0](#))
- Post-surgery restaging (Post-Surgery and prior to first cycle of FOLFOX)
- Post 4 Cycles of FOLFOX
- Post-Treatment Follow-Ups (every 16 weeks +/- 28 days after completion of treatment for 24 months post-registration or until documented progression, whichever occurs first)

All scans must be submitted digitally. CD/DVD shipment of images is **not** allowed.

6.4.2.1 Real-time Review Scan Submission and Timeframes

The complete CT/MRI scan in digital **DICOM** format will be submitted to Alliance Imaging Core Laboratory at IROC Ohio within no more than 3 business days after acquisition completeness or pre-registration. BMP files, JPG files, or hard copies (films) are not acceptable. The raw data of

the entire study should be saved until the scan is accepted by the Imaging Core Laboratory. The Imaging Core Lab will notify site and Alliance A021501 imaging committee within **2 business days** of the data receipt as well as within **3 business days** of the quality check report upon data receipt.

Sites need to de-identify the patient data using institutional procedures to remove patient name and medical record number while preserving the Alliance patient ID number (e.g. 112136) and protocol number (e.g. A021501), respectively.

For baseline staging and pre-surgical restaging CT/MR scans, imaging data must be submitted to the Imaging Core Lab **electronically** via TRIAD, Web-based data transfer, or FTP data transfer approaches for real-time central review purposes. For patients that consent to A021501-IM1, CT/MRI images will be collected digitally for the research described in [Section 14.2](#).

TRIAD data transfer: see [Section 4.1.1](#) for details. Additional information is available at <http://triadhelp.acr.org/ClinicalTrials/NCISponsoredTrials.aspx>

6.4.2.2 Web-based Data Transfer

Any PCs with Internet access can be used to upload images to the Imaging Core Lab via this approach. The standard Web access information will be provided separately through the specific trial e-mail [REDACTED] per the request by participating sites before their first data submission.

6.4.2.3 FTP Transfer

Any FTP software can be used to upload images to the secure FTP Server of the Imaging Core Laboratory. The standard FTP access information will be provided separately through the specific trial e-mail [REDACTED] per the request by participating sites before their first data submission.

De-identified local scan interpretation reports must be sent along with all image submissions. These de-identified reports can be sent to the ICL at IROC Ohio via [REDACTED]

Send an e-mail notification to inform the Imaging Core Lab at [REDACTED] of the imaging data submission once the data transfer is complete. Any questions or problems about the data transfer to the Imaging Core Lab, call the Core Lab IT group at [REDACTED] for help.

Please note, institutions located in states with dosimetry reporting requirements specified by state law must include dosimetry data in the final imaging report.

7.0 TREATMENT PLAN/INTERVENTION

NOTE: Arm 2 closed to new patient enrollment on 08/13/2018, and further Arm 2 treatment for enrolled patients ceased as of 08/13/2018.

Protocol treatment is to begin \leq 14 days of registration.

For questions regarding treatment, please see the study contacts page.

It is acceptable for individual chemotherapy doses to be delivered \leq a 24-hour (business day) window before and after the protocol-defined date for Day 1 of a new cycle. For example, if the treatment due date is a Friday, the window for treatment includes the preceding Thursday through the following Monday. In addition, patients are permitted to have a new cycle of chemotherapy delayed up to 7 days for major life events (e.g., serious illness in a family member, major holiday, vacation that cannot be rescheduled) without this being considered a protocol violation. Documentation to justify this delay should be provided.

Surgery and imaging will be conducted at the registering institution. Radiation therapy must be performed at a radiation therapy facility participating in the IROC monitoring program. Chemotherapy may be given at a non-registering institution. All protocol conduct must be followed and the registering institution is responsible for ensuring all data is reported per protocol. Please refer to the Alliance policy and procedures document posted on the Alliance website for the policy on engagement in research by non-registering institutions. If the NCTN Group credited for enrollment is a non-Alliance Group, then other requirements from the credited Group may apply.

Patients will be randomized to either Arm 1 or Arm 2 (closed to new patient enrollment on 08/13/2018) of the study. Patients will progress through treatment in the absence of any criteria described in [Section 12.1.3](#).

Patients on both Arm 1 and Arm 2 will receive 4 cycles of mFOLFIRINOX and then undergo restaging imaging studies, as per [Section 7.4.1](#). These scans are NOT centrally reviewed.

After the first set of restaging scans, patients who do not show progression on the local read per [Section 12.1.3](#) will be treated as follows: patients on Arm 1 will receive 4 additional cycles of mFOLFIRINOX, and patients on Arm 2 will receive 3 additional cycles of mFOLFIRINOX and then hypofractionated radiotherapy per [Section 7.2](#). These additional cycles of mFOLFIRINOX for both Arm 1 and Arm 2 should start within 14 days after cycle 4 day 1 unless dose modifications indicate delay.

After preoperative therapy is completed, patients will be restaged, and, if still considered a surgical candidate for resection per the criteria of [Section 3.2.1](#) after central review, will proceed to surgery per [Section 7.3](#). Surgery must occur 4 to 8 weeks after last dose chemotherapy (Arm 1) or of radiation (Arm 2).

Patients considered inappropriate for surgery will go off of study treatment, and are to be followed per the follow-up schedule provided in the study calendar ([Section 5.0](#)).

Following surgery, patients will receive post-operative chemotherapy with 4 cycles of FOLFOX starting 4 to 12 weeks from date of surgery.

Treatment will continue until disease progression or unacceptable adverse event or inability to tolerate treatment even with all allowed dose reductions, or completion of the full treatment program and entrance onto clinical follow-up. Also, see Sections [12.1.3](#) and [12.3](#) for additional information regarding discontinuation of treatment.

See [Section 8.1](#) for ancillary/concomitant therapy guidelines.

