
The CTSU website is located at https://www.ctsuo.org.
		

PREOPERATIVE EXTENDED CHEMOTHERAPY VS. CHEMOTHERAPY PLUS HYPOFRACTIONATED RADIATION THERAPY FOR BORDERLINE RESECTABLE ADENOCARCINOMA OF THE HEAD OF THE PANCREAS

Pre-Registration Eligibility Criteria (see [Section 3.2.1](#))

Cytologic or histologic proof of adenocarcinoma of the pancreatic head or uncinate process.
 TNM Stage: T1-4N0-1orNxM0
 Local radiographic reading consistent with borderline resectable cancer of the pancreatic head

[figure not shown]
Registration Eligibility Criteria (see [Section 3.3](#))

Confirmation of radiographic stage as borderline resectable by central radiographic review
 No prior chemotherapy or radiation for pancreatic cancer and no definitive resection of pancreatic cancer
 No strong CYP3A4 inhibitors or inducers (See [Section 3.3.3](#))
 No grade ≥ 2 neuropathy
 No known Gilbert’s Syndrome or known homozygosity for UGAT1A1*28 polymorphism.
 No uncontrolled gastric ulcer disease (Grade 3 gastric ulcer disease) within 28 days of registration
 Not pregnant and not nursing, because this study involves an agent that has known genotoxic, mutagenic and teratogenic effects.
 Age ≥ 18 years
 ECOG Performance Status 0 or 1

Required Initial Laboratory Values	
Absolute neutrophil count (ANC)	≥ 1500/mm ³
Platelet Count	≥ 100,000/mm ³
Creatinine	≤ 1.5 x upper limit of normal (ULN)
Calc. Creatinine or Clearance (see Alliance website)	> 45 mL/min
Total Bilirubin	≤ 2.0 x mg/dL
AST / ALT	≤ 2.5 x ULN

Schema

As of 08/13/2018, patients will no longer be registered/randomized to Arm 2.

* RT simulation and EUS/ fiducial marker placement is performed during cycle 5 or 6 of mFOLFIRINOX

Surgery and imaging must be conducted at the registering institution. Radiation therapy must be performed at a facility participating in the IROC monitoring program. Chemotherapy may be given at a non-registering institution. If the NCTN Group credited for enrollment is a non-Alliance Group, then other requirements from the credited Group may apply. All protocol conduct must be followed and the registering institution is responsible for ensuring all data is reported per protocol.

Treatment is to continue until disease progression or unacceptable adverse event. Patients will be followed for 5 years or until death, whichever comes first.

Please refer to the full protocol text for a complete description of the eligibility criteria ([Section 3.0](#)) and treatment plan ([Section 7.0](#)).

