1.2 Rationale for Trial Design

Herein we propose to evaluate the efficacy of two rational neoadjuvant treatment backbones in a randomized study. The study builds upon our previous work as requested by CTEP and will define standard preoperative treatment regimens to which future novel regimens can and will be compared in subsequent randomized trials.

We have proposed a randomized frequentist design using exact binomial distribution for this study. This design focuses on evaluating whether clinically meaningful improvement of survival rate can be achieved by the tested regimens comparing to historical data. The evaluation of each treatment arm will be conducted separately, based on a practical assessment of whether the arm is “clinically relevant” alone, as well as the outcome comparisons between two treatments if both arms are deemed promising at the end of the trial. This study uses a critically important interim endpoint (R0 resection rate) that is different from the final endpoint (18 month OS rate) and an interim analysis which allows elimination of any futile arm after only 30 patients enrolled to that arm. If both arms are deemed promising at the end of the trial, a pick-a-winner strategy will be employed to choose one arm as the “winner”. Using a fast maturing end point, R0 resection rate, for interim analysis prevent the possibility of halting the trial at interim analysis while the whole study still powered to detect clinical meaningful improvement in OS rate.

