2.2 Secondary Objectives

- 2.2.1 To evaluate and estimate the R0 resection rates in patients receiving each of the two multimodality treatment regimens.
- 2.2.2 To evaluate and estimate the event-free survival in patients receiving each of the two multimodality treatment regimens.
- 2.2.3 To evaluate and estimate the pathologic complete response (pCR) rates in patients receiving each of the two multimodality treatment regimens
- 2.2.4 To assess the adverse events (AE) profile and safety of each treatment arm, using the CTCAE and PRO-CTCAE.

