6.2 Specimen Collection and Submission

For all patients registered to Alliance A021501: Retrospective histopathology review will be conducted using a representative paraffin embedded block of pancreatic tumor from the surgical resection specimens. If the surgical resection specimen does not show residual cancer, the specimen from the diagnostic biopsy or a representative FNA cytologic slide should be submitted in addition to the surgical specimen. **The submission of tumor (or diagnostic pathology specimen for patients that have a pCR at surgery) for histopathology review is**

required for all patients registered to this study, including those who are found to be ineligible and those who do not receive protocol therapy.

For patients registered to substudy A021501-PP1: All participating institutions must ask patients for their consent to participate in the correlative substudies planned for Alliance A021501-PP1, although patient participation is optional. Biomarker and pharmacogenetic studies will be performed. Rationale and methods for the scientific components of this study is described in [Section 14.1](#).

For patients who consent to participate, specimens will be collected at the time points listed in the table below:

	Prior to Initiation of Treatment	At surgery	Storage/ Shipping	Submit to:
Mandatory for all patients on A021501:				
Paraffin block AND one stained H&E slide	A	X	Ambient temp/ ship overnight	WUSTL
To be submitted ONLY for patients that consent to A021501-PP1*:				
Whole blood¹ (EDTA/lavender top)	1 x 10 mL		Cool pack/ship overnight	WUSTL
To be submitted ONLY for patients that consent to biobanking for future research**:				
Paraffin block	A		Ambient temp/ ship overnight	WUSTL

- * Patients who consent to A021501-PP1 are those who answer “Yes” to the model consent question, “I agree to have my blood specimen collected and I agree that my specimen samples and related information may be used for the laboratory studies described above.”
- ** Patients who consent to biobanking for future research are those who answer “Yes” to the model consent question, “My samples and related information may be kept in a Biobank for use in future health research.”

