12.1.2 Disease Progression

Remove from protocol therapy any patient with disease progression as per [Section 12.1.3](#) or recurrence after surgery (either Arm 1 or Arm 2 patients). Document details, including tumor measurements, on data forms.

After disease progression, patients should be followed for survival per the study calendar ([Section 5.0](#)).

Note: Biochemical progression (B-PROG) without the demonstration of objective progression (PD) of target or non-target lesion will not be sufficient indication to remove the patient from the study (see [Section 11.4.3](#)).

12.1.3 Removal of Patients from Protocol Therapy:

In the absence of treatment delays due to adverse events, treatment will be completed unless the patient experiences any one of the following scenarios. The specific indication should be described as:

- Metastatic disease identified on imaging studies
- For patients with RECIST PD with local progression only, the treating investigator should decide whether continuing protocol treatment is in the best interest of the patient
- The presence of locally advanced disease on pre-surgical restaging imaging studies (see [Appendix II](#) for definition of locally advanced pancreatic cancer)
- Decline in PS in the absence of radiographic evidence for disease progression if PS cannot be recovered (symptomatic deterioration)
- Metastatic disease identified intraoperatively and biopsy-proven
- Unresectable disease identified intraoperatively (e.g., locally infiltrative disease without metastases for which the surgeon does not feel resection is safe)
- R2 surgical resection
- Nontherapeutic (aborted) operation for any other reason
- Intercurrent illness that prevents further administration of treatment
- Unacceptable adverse event(s)
- Patient decides to withdraw from the study
- General or specific changes in the patient's condition that render the patient unacceptable for further treatment in the judgment of the investigator

Patient should be removed from protocol therapy, and followed as per [Section 5.0](#), post-treatment follow-up. Protocol treatment will be discontinued and further treatment is at the discretion of the treating physician.

12.1.4 Follow-up for Patients Removed from Protocol Therapy:

For patients who are removed from protocol therapy in any instance listed in [Section 12.1.3](#), follow patients per the schedule found in [Section 5.0](#) of the protocol for clinical and survival status.

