13.0 STATISTICAL CONSIDERATIONS

Note: Arm 2 closed to new patient enrollment on 08/13/2018.

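### Arm 2 stopped on 08/13/2018, but Section 13.4 still compares the arms with no limit to concurrently randomized patients, and its 18-month OS chi-squared test lacks the gate that Section 13.3 sets

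*Combined protocol and SAP*

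**What the plan says.** **The closure.** The Schema states: "As of 08/13/2018, patients will no longer be registered/randomized to Arm 2". Section 7.0 repeats the closure and adds that "further Arm 2 treatment for enrolled patients ceased as of 08/13/2018"; Section 7.2 says the same. The note at the head of Section 13.0 reads only: "Arm 2 closed to new patient enrollment on 08/13/2018". Nothing in Section 13 mentions that treatment also stopped.

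**The gate.** Section 13.3 permits the OS comparison between arms only when both are judged promising at the end. Section 1.2, which is rationale, is looser: it describes separate evaluation of each arm, together with "the outcome comparisons between two treatments if both arms are deemed promising at the end of the trial". Under Section 13.4.1.2 an arm passes if it reaches full accrual and at least 36 of 62 evaluable patients are alive at 18 months; otherwise it is deemed inefficacious.

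**The tests.** Section 13.4.1.3 prescribes a chi-squared (or Fisher) comparison of 18-month OS rates with no condition. Its next paragraph makes the OS log-rank test conditional on both arms passing. Sections 13.4.2.1 to 13.4.2.4 compare EFS, R0, pCR and adverse events between arms with no condition.

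**The population.** Section 13.1.1 counts as evaluable anyone who consented, was found eligible on central review and received any protocol treatment. Cohort 1 for R0 and pCR (13.1.2.1, 13.1.2.3) uses the same criteria, and cohort 2 is the patients who had surgery. The EFS and adverse event sections name no other population. None of these sets a date limit.

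**The concern.** From 08/13/2018 a new patient could enter only Arm 1. Later Arm 1 patients therefore have no randomized counterpart, and a test that includes them mixes a randomized contrast with a comparison across calendar time. A reader of the report could take such a p-value as a randomized comparison of two completed regimens, although part of Arm 1 was not concurrent and part of Arm 2 may have been stopped by date.

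The plan also gives two answers on whether the 18-month OS rates are compared at all if Arm 2 fails or falls short. Leaving that choice, and the choice of which Arm 1 patients to include, until the data are known invites selective reporting.

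**Working it through.** **1. The plan's own figures.** Per-arm rule, exact binomial: P(X ≥ 36 | n = 62, p = 0.63) = 0.826. Interim stopping, P(X ≤ 11 | n = 30), is 0.431 at R0 40% and 0.0083 at R0 60%. Power with the interim at R0 60%, taking R0 and OS as independent, is 0.826 × (1 − 0.0083) = 0.819. Section 13.3 states 82%, 43% and 0.8%, so these reproduce. All are per-arm figures; the plan gives no power for any between-arm test.

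**2. The tests side by side.**

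| Test | Section | Both-arms gate | Date limit |
|---|---|---|---|
| 18-month OS rate, chi-squared/Fisher | 13.4.1.3, first paragraph | none | none |
| OS log-rank, pick-the-winner | 13.4.1.3, second paragraph | yes | none |
| EFS log-rank | 13.4.2.1 | none | none |
| R0, pCR, adverse events | 13.4.2.2 to 13.4.2.4 | none | none |

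The first row conflicts with Section 13.3. If Arm 2 closed below 62 evaluable patients, the full-accrual condition in 13.4.1.2 fails; below 36, having 36 alive is impossible as well. Section 13.3 then says no OS comparison, and 13.4.1.3 says run one. The lower two rows conflict only with the looser wording of Section 1.2.

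**3. Share of non-concurrent Arm 1 patients.** Assume m per arm at closure and a final Arm 1 of 62 evaluable to 67 accrued (Section 13.2). The share is (N − m)/N.
- m = 40: 22/62 = 35%; 27/67 = 40%.
- m = 60: 2/62 = 3%; 7/67 = 10%.

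**4. What drift would do.** Assume 18-month OS is 50% in both arms and d points higher in later Arm 1 patients, with Arm 1 at 62. The expected difference shifts by d × (62 − m)/62. Type I error is by exact enumeration of the uncorrected two-sided 5% chi-squared test.

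| m | d = 0: error | d = 10: shift, error | d = 20: shift, error |
|---|---|---|---|
| 30 | 4.6% | 5.2 points, 7.1% | 10.3 points, 15.0% |
| 40 | 4.8% | 3.5 points, 6.2% | 7.1 points, 10.5% |
| 50 | 5.1% | 1.9 points, 5.6% | 3.9 points, 7.0% |

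Both m and d are assumptions; the documents give neither.

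**5. Power cost of a concurrency limit.** Same test, 63% vs 50%. The planned 62 vs 62 gives 33%.

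| Arm 2 size (assumed) | All Arm 1 (62) | Concurrent only |
|---|---|---|
| 30 | 22% | 17.5% |
| 40 | 26% | 23% |
| 50 | 29% | 27% |

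**6. Arm 2 patients stopped by date.** From treatment start to surgery in Arm 2: 12 weeks to the cycle 7 dose, about 1 week to radiation (Section 7.2.1.2 gives a 5-day minimum; 1 week is assumed), 1 to 2 weeks of radiation (7.2.1.3) and 4 to 8 weeks to surgery ("Surgery must occur 4 to 8 weeks after last dose chemotherapy (Arm 1) or of radiation (Arm 2"). The sum is 18 to 23 weeks. At 2 patients per month in Arm 2 (half of the 4 in Section 13.2), or 2 × 12/52 = 0.46 per week, that is 8.3 to 10.6 patients. So about 8 to 11 could have been between first dose and surgery on the closure date, before drop-outs and if accrual had not been paused. This shows only that the number is worth reporting.

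**The case against.** The case on the other side is strong on scope, and much of it stands.

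- A reader might infer that no between-arm test of any kind is allowed. Section 13.3 gates OS only, and the Section 1.2 sentence is rationale that does not say comparisons happen only under that condition. Ungated secondary and safety tests do not contradict Section 13.3.
- A reader might infer that Arm 2 patients stopped by date have no place in the analysis. The definitions in 13.1.1, 13.1.2.1 and 13.1.2.3 keep them in the denominators, and Section 5.0 requires survival follow-up after removal from treatment.
- A reader might infer that Arm 2's R0 and pCR rates must read low. The R0 definition is not confined to protocol surgery, so a later R0 resection counts as worded. Section 6.2 requires tumor submission from all registered patients, "including those who are found to be ineligible and those who do not receive protocol therapy". Cohort 2 already gives an estimate not diluted by patients stopped before surgery, and 13.4.2.2 and 13.4.2.3 plan both cohorts.
- A reader might infer that Arm 2 crossed the R0 futility rule. The documents give no reason for the closure, and the rule in 13.4.1.1 only ends accrual, so nothing can be built on that.
- No decision rule is touched.

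What the objection does not answer is the absence of a date limit in every between-arm test, and the contradiction between Section 13.3 and the chi-squared sentence in 13.4.1.3. That Arm 1 stayed open is implied rather than stated: every closure note names Arm 2 alone.

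**Conclusion.** The point holds in a limited form. As written, the comparisons of 18-month OS, EFS, R0, pCR and adverse events admit Arm 1 patients who were never randomized against Arm 2. The 18-month OS chi-squared test also contradicts the OS gate in Section 13.3 if Arm 2 closed below full accrual. The secondary tests are at odds only with the looser statement in Section 1.2.

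The size is unknown. Depending on the assumed closure point (60 or 40 per arm), 3% to 40% of Arm 1 would be non-concurrent. The distortion is negligible without drift and becomes material only with an early closure and large drift. The direction for OS and EFS cannot be stated.

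The conclusion rests on the text and on Arm 1 having enrolled after closure. It does not reach Arm 1's primary decision, the gated log-rank test or pick-the-winner, and it does not show that Arm 2's own estimates are biased.

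**What to change.** In Section 13.4:

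1. Put the 18-month OS chi-squared test under the same gate as the log-rank test, or state that it is descriptive. This reconciles it with Section 13.3.
2. Restrict any between-arm analysis to patients randomized while both arms were open (before 08/13/2018) and label it descriptive. Report later Arm 1 patients in the single-arm Arm 1 results only.
3. Report how many Arm 2 patients had treatment stopped by the closure and in which phase. Analyse OS and EFS as assigned, without censoring at closure. Present Arm 2 cohort 1 R0 and pCR beside cohort 2, with that caveat. For EFS, state which progression data exist after closure: Section 5.0 asks only for survival information from patients removed from treatment, while 12.1.4 asks for clinical and survival status.

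The cost is a few sentences, a date filter and one count table. The statistical price is about 1 to 4 points of power (step 5 of the working), in a comparison with only 33% power even at the planned size.
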